7.3 Other collected variables

Participant characteristics are collected at baseline. These characteristics are participant age, sex, ethnicity, index of multiple deprivation, type of SMI, date diagnosed with SMI and date diagnosed with diabetes.

Intervention use data are collected: number of coaching sessions, session duration, content of sessions and use of the Change One Thing app.

Any adverse events (AEs) or serious adverse events (SAEs) will be reported to the Chief Investigator and will be reviewed by a clinician independent to the DIAMONDS study team. The reporting period will be from study entry up to the last follow-up visit. Details about AEs/SAEs will be captured at each clinical contact point or study assessment. AEs/SAEs that might have occurred since the previous visit or assessment are elicited from the participant by open questioning and recorded. All events related to the DIAMONDS intervention will be recorded on adverse events forms. Further information may be requested for follow up of these events. Detailed records will be kept of all adverse events.

8 Data

8.1 Case Report Forms

There are multiple CRFs, the table below shows when they should be completed:

CRF	Baseline	6-Months	12-Months	When needed
Bloods	X	Х	Х	
Investigator	Х	Х	Х	
Participant	Х	Х	Х	
Mechanisms of	Х	Х	Х	
Action (MoA)*				

Table 3: CRF schedule

Change of Status (CoS)			Х
Adverse events & serious adverse events			Х
Eligibility	Х		

*There is also a monthly MoA CRF

The baseline participant CRF includes a section on demographics that is not in the follow up versions.

Trained members of the R&D team are sent paper copies of the CRFs to fill out and return by post. The CRFs will be completed in person but if needed, will be completed over the phone or by post. YTU will process the CRFs when received. CRFs can be found in: "\\hsci.york.ac.uk\hsciytu\Project -- DIAMONDS - Statistics\1 Statistics\WP4 - RCT\Documentation\CRFs".

8.2 External datasets

8.2.1 Intervention delivery

Data on the delivery of the intervention will be collected via Qualtrics and the Change One Thing app:

- Session duration;
- Number of sessions delivered;
- Mode of delivery (remote, phone, in person): frequencies/percentages;
- List of content areas with number of participants who discussed each content area;
- Duration a participant stayed with the same action plan/content area;
- Number of content areas covered during total intervention period and workbook and/or Change One Thing app.

9 Sample Size

Original sample size calculation

The sample size calculation was based on detecting a clinically meaningful difference of 5.5 mmol/mol (0.5%) in HbA1c at 12 months. This difference was selected based on data from trials of diabetes self-management in the general diabetes population and NICE guideline on type 2 diabetes management. Based on the variation observed in HbA1c in a Clinical Practice Research Datalink (CPRD) population study, we assumed a standard deviation of 15.3 mmol/mol. Based on attrition rates in previous severe mental illness trials, we expect approximately 20% attrition. In the intervention arm, a DIAMONDS Coach will deliver the intervention to multiple participants, and therefore the outcomes of participants with the same coach may be correlated. Although only a small clustering effect is expected, this provides a more conservative sample size estimate. The sample size was therefore adjusted for clustering in the intervention arm.

For approximately 90% power, at the 5% significance level, assuming an average cluster size of 10-12 participants per DIAMONDS coach with an intraclass correlation (ICC) of 0.02 in the intervention

DIAMONDS Statistical Analysis Plan version 1 Page | 10 arm, and adjusting for 20% attrition, we estimate we will need to randomise 450 participants, with 225 per treatment group.

Revised sample size calculation

In February 2024 following discussion with the TSC, an amendment was made to the original sample size calculation described above due to slower than anticipated recruitment. We amended the sample size by including an adjustment for the correlation between baseline and 12-month HbA1c (0.3) to reflect the repeated measures analysis model planned for the primary analysis. This led to a minimum sample size of 380 participants needed; keeping all other assumptions the same would achieve 88% power. However, we will continue recruiting beyond this minimum target until the end of the agreed recruitment window.

10 Randomisation and blinding

As stated in the protocol:

Consenting participants will be randomised on a 1:1 allocation ratio to either the DIAMONDS intervention or the usual care group using computer generated permuted blocks of random sizes. Randomisation will be carried out by York Trials Unit (YTU) independently of the R&D team using a secure, online randomisation service to ensure allocation concealment.

The DIAMONDS Programme Manager and Trial Coordinators will be unblinded to allocation in order to facilitate contact between randomised participants and their designated DIAMONDS Coach, if required. Following randomisation, the participating site will contact DIAMONDS Coaches to advise them to approach participants randomised to the intervention group to arrange the first intervention session.

Statisticians will not remain blind during the study but will not see any unblinded primary outcome data until a version 1 of the statistical analysis plan has been signed off.

11 Analysis of internal pilot trial/phase

As stated in the protocol:

Recruitment rate and the 95% confidence interval will be estimated from the pilot data collected. A CONSORT diagram will produced with the following outcomes: number of eligible participants; proportion of eligible participants approached for consent; proportion of eligible participants not approached and reasons why; proportion of participants approached who provide consent; proportion of participants approached who do not provide consent; proportion of participants providing consent who are randomised; proportion of participants randomised who do not receive the randomly allocated treatment; proportion of participants dropping out between randomisation and follow-up.

Reasons why eligible participants were not approached; reasons for participants declining to participate in the study; reasons why randomised participants did not receive their allocated treatment and reasons for dropout will be summarised if available.

Results will be compared against the recruitment assumptions and progression targets, and continuation of the trial and any appropriate adaptations to the trial will be decided by the Steering Committee and the funding body.

DIAMONDS Statistical Analysis Plan version 1 Page | 11 Progression from the pilot phase to the main trial will depend on satisfying the following prespecified targets at 12 months from the start of the trial:

	Green	Amber	Red
a) Average number of participants per site per month	2 participant per month	1.3 to <2 participants per month	<1.3 participants per month
b) Recruitment of sites	15 sites	10 to 14 sites	<10 sites
c) Completeness of	80% of participants	65% to <80% of	<65% of participants
outcome (HbA1c) data at	with complete	participants with	with complete
6-months	outcome	complete outcome	outcome

The following actions will be taken based on the targets achieved above:

- Green: continue the trial without any adaptations.
- Amber: review procedures to identify underlying problems, and put in place strategies to address these, review after an interval and terminate the trial if recruitment trajectory does not indicate that full recruitment will occur within scheduled recruitment period.
- Red: terminate the trial unless we can confidently identify successful strategies or rapidly resolve the problem.

The internal pilot had been completed at the time of writing the statistical analysis plan.

12 Final analysis

12.1 Analysis software

All analyses will be conducted in the most recent version of Stata (7) or R(8).

12.2 Analysis principles and populations

Analysis of primary and secondary outcomes will be intention-to-treat (ITT) (unless otherwise stated) and tests will be two sided at 5% significance level.

12.3 Screening, eligibility, recruitment and follow-up data

A CONSORT flow diagram will be presented (Ref: Figure 1). Tables will be presented with reasons for participant ineligibility and withdrawal. Recruitment numbers will be reported by site and allocation arm. CRF return rates will also be reported.

12.4 Baseline data

Baseline characteristics will be reported descriptively by randomised group (Ref: Tables 2-3). Continuous data will be summarised as means, standard deviations (SD), medians and interquartile ranges (IQR), and categorical data will be summarised as frequencies and percentages. No formal statistical comparisons of baseline data will be undertaken. Data will be reviewed, and any imbalance reported.

Participant demographic information (e.g. age, gender, ethnicity, etc), other key characteristics (type of SMI diagnosis, whether single or multiple SMI diagnoses, whether SMI or diabetes was diagnosed first, smoking status, insulin use etc) and baseline measures will be summarised by randomised group.

12.5 Intervention delivery

Participants randomised to the DIAMONDS Intervention will be offered individual sessions over a sixmonth period with a DIAMONDS Coach. Within the six-month period, the Coach and participant will have the flexibility to meet as often as they both would like. Summaries of the intervention delivery will be presented in tables and graphically (Ref: Table 6, Fig 2) and will include:

- Number of sessions received (mean, SD, median, IQR);
- Number of participants who attended at least 1 session;
- Session duration (mean, SD, median, IQR);
- Number and percentage of the mode of delivery of sessions (remote, phone, in person);
- Number and percentage of participants who discussed each content area;
- Average duration a participant stayed with the same action plan/content area;
- Average number of content areas covered during total intervention period and workbook and/or Change One Thing app.

12.6 Primary analysis

The primary outcome (HbA1c at 12-month post-randomisation) will be analysed using a partiallynested mixed effects regression model, with HbA1c scores at 6- and 12-months follow-up as the dependent variable, adjusting for baseline HbA1c scores and outcome source (central lab or medical records), randomised treatment group, time and a treatment group-by-time interaction will be included as fixed effects and participant and DIAMONDS coach as a random effect nested within treatment arm (9). Different covariance patterns for the repeated measurements will be explored and the most appropriate pattern will be used for the final model. Diagnostics including Akaike's information criterion will be compared for each model (smaller values are preferred). The model assumptions (normality of residuals, homoskedasticity and multicollinearity) will be evaluated using residual plots and calculating variance inflation factors (VIFs).

The estimated treatment group difference at 12 months will be reported as the primary endpoint with the associated 95% confidence interval and p-value (Ref: Table 7). Analysis of the primary outcome will be checked by a second statistician. The analysis model does not match exactly the method used in the sample size calculation which simply compares one follow up point (12 months) with an adjustment for baseline correlation. This is a more conservative approach so we should still have adequate power for the primary analysis.

HbA1c is being collected from different sources:

Central laboratory- participant must consent to bloods being taken at their visit. The sample is then sent to a central laboratory in Manchester. Blood results are returned to YTU and recorded on a Bloods CRF by YTU staff.

Medical records- if lab results are unavailable (e.g. participant refuses to have blood samples taken), the investigator may use medical records to look up a recent blood test result and corresponding date which will be recorded on that CRF (baseline, Month 6 or Month 12).

DIAMONDS Statistical Analysis Plan version 1 Page | 13 The primary analysis will include all HbA1c values from both sources providing they are within +/-6 weeks from the date of the specified timepoint (baseline, 6- and 12-months post randomisation). Values outside of this window will be counted as missing. We will conduct analyses with all observed data. Mixed effects regression models use all available data and assume missing outcome data are missing at random. To explore this assumption, we will summarise the baseline characteristics of participants with and without missing outcome data and further sensitivity analyses are outlined in section 12.7.

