12.7.2 Missing data

The amount of missing data will be reported for each randomised arm, and we will also compare the baseline characteristics of participants who are included in the primary analysis to ensure that any attrition has not produced any imbalance in the groups in important covariates. We will explore the extent and pattern of missing data and, if appropriate, will undertake multiple imputation to assess the impact of missing data on treatment effect estimates.

Multiple Imputation by Chained Equation (MICE) will be used as the method for imputation (10)(11). The imputation model that will be used to impute Hba1c at baseline, 6 months and 12 months. We will present results from the following models:

Baseline imputed only- the imputation model will include HbA1c at baseline and 6 months, age, sex, ethnicity, IMD decile and treatment arm. Thirty multiply imputed data sets will be used. Missing 12-month HbA1c values will be imputed but removed again before analysis (12)

Baseline and 12 months- the same model described above will be used and the imputed 12-month HbA1c values will remain.

Treatment effects and their 95% CIs will be presented in a forest plot alongside those produced using the primary analysis methods and other sensitivity analyses (Ref: Table 7).

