12.8 Subgroup analyses

Subgroup analyses will be performed to explore the potential effect of the following subgroups:

- Participants with good and those with suboptimal diabetes control at baseline as defined as High control (HbA1c values <= 58 mmol/mol) and Low control (HbA1c values >58 mmol/mol)
- Ethnicity (White, Asian or Asian British, Black, Black British, Caribbean or African, Mixed or multiple ethnic groups or Other Ethnic background)
- Insulin use status (Prescribed insulin Yes or No)
- Urdu speakers (Yes or No)

DIAMONDS Statistical Analysis Plan version 1

As we are unable to predetermine the numbers in each subgroup, the completion of each subgroup analysis will be subject to there being sufficient numbers in the group.

The primary analysis model will be refitted with an interaction term between the randomisation group and the specified subgroup variable. Treatment effect for these subgroups will be reported as adjusted mean differences with their associated 95% CI and p-values (Ref: Table 8). As recommended by the literature, the subgroup analysis will be restricted to the primary analysis

and subgroups will be defined by baseline data i.e. data that is not dependent on the intervention(14). Subgroup analysis will be performed regardless of the results of the primary analysis.

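### The primary model leaves out baseline insulin use and diabetes duration, both already collected: a modest missed gain in precision, not an error

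*SAP*

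**What the plan says.** SAP 12.6 fits HbA1c at 6 and 12 months in a partially nested mixed model, "adjusting for baseline HbA1c scores and outcome source (central lab or medical records), randomised treatment group, time and a treatment group-by-time interaction", with participant and coach as random effects. Outcome source describes how the value was obtained, so baseline HbA1c is the only prognostic baseline covariate.

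Section 9 revises the sample size using the "correlation between baseline and 12-month HbA1c (0.3", which gives a minimum of 380 and 88% power, and says recruitment will continue past that minimum.

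The two omitted variables appear elsewhere in the SAP:
- Insulin use is self-reported (7.2), is named among the key characteristics to be summarised by arm (12.4), and is a subgroup factor, "Insulin use status (Prescribed insulin Yes or No" (12.8).
- Section 7.3 lists "date diagnosed with SMI and date diagnosed with diabetes" among the baseline characteristics, and the template for Table 2 has a row for time since diabetes diagnosis.

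For missing data (12.7.2), "the imputation model will include HbA1c at baseline and 6 months, age, sex, ethnicity, IMD decile and treatment arm". Neither insulin use nor diabetes duration is included there.

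**The concern.** In a linear model, a baseline variable that predicts the outcome beyond baseline HbA1c removes residual variance from the treatment contrast. On the plan's own assumption, 91% of the variance remains after adjustment for HbA1c. Insulin use and diabetes duration are plausible candidates for part of it, are already on the case report forms, and cost nothing further to collect. The minimum target was lowered from 450 to 380 because recruitment was slow, so precision that is free is worth taking.

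The SAP also has no prespecified adjustment if the arms differ on insulin use: 12.4 only reports an imbalance. Any adjustment made later would be post hoc. The imputation model has a similar gap. If either variable is related both to HbA1c and to dropout, leaving it out weakens the missing-at-random assumption on which 12.7.2 relies.

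**Working it through.** **Inputs from the SAP (sections 9 and 12.2).**
- Difference: "detecting a clinically meaningful difference of 5.5 mmol/mol (0.5%) in HbA1c at 12 months"
- SD: "we assumed a standard deviation of 15.3 mmol/mol"
- Baseline to 12-month correlation: 0.3
- ICC: 0.02, in the intervention arm only
- Cluster size: 10-12 per coach (11 used here)
- Attrition: 20%
- Minimum randomised: 380
- Test: "tests will be two sided at 5% significance level"

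**Step 1: reproduce the stated power.**
- Analysed per arm = 380/2 × 0.8 = 152.
- Design effect in the intervention arm = 1 + (11 − 1) × 0.02 = 1.2.
- Residual variance = 15.3² × (1 − 0.3²) = 234.09 × 0.91 = 213.0.
- SE = √(213.0 × (1.2 + 1)/152) = 1.756.
- Power = Φ(5.5/1.756 − 1.96) = 87.9%, against 88% stated.
- Cluster sizes of 10 and 12 give 88.2% and 87.7%. The plan's figure reproduces without any further covariate.

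**Step 2: what insulin use could add.** The SAP does not say how many participants use insulin, or how far their 12-month HbA1c differs at equal baseline HbA1c. Both are assumed here: a proportion p of 20-40% and a gap of 3-10 mmol/mol.
- Variance due to insulin use = gap² × p(1 − p).
- Fraction of residual variance f = that variance / 213.0.
- New SE = 1.756 × √(1 − f).
- Equivalent number randomised = 380/(1 − f).

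| Gap (mmol/mol) | p | f | Power | Equivalent N |
|---|---|---|---|---|
| none | – | 0 | 87.9% | 380 |
| 3 | 0.2 | 0.7% | 88.2% | 383 |
| 3 | 0.3 | 0.9% | 88.2% | 383 |
| 6 | 0.2 | 2.7% | 88.8% | 391 |
| 6 | 0.3 | 3.5% | 89.1% | 394 |
| 8 | 0.3 | 6.3% | 89.9% | 406 |
| 10 | 0.3 | 9.9% | 91.0% | 422 |
| 10 | 0.4 | 11.3% | 91.4% | 428 |

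The 95% confidence half-width goes from 1.96 × 1.756 = 3.44 mmol/mol to 3.43 at the smallest case and 3.24 at the largest.

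**Step 3: chance imbalance is the same variance.** At 30% users and a gap of 10, chance imbalance contributes 1.96 × 10 × √(2 × 0.3 × 0.7/152) = ±1.03 mmol/mol to the estimate. The underlying variance, 21.0 × 2/152 = 0.276, already lies inside the squared SE. Apart from the clustering factor (2.2 in place of 2), it is the reduction counted in step 2: 21.0 × 2.2/152 = 0.304 = 1.756² − 1.667². It must not be added as a second effect.

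**Step 4: sensitivity to the correlation.** The 0.3 is a planning value. If the true correlation is 0.5, power at 380 is already about 93% and there is less to gain.

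**The case against.** The strongest reply is that nothing here is wrong. The model is prespecified, adjusts for the baseline value of the outcome, and meets its stated power without the extra covariates. The size of the gain rests on assumed inputs, and at a gap of 3 it is about 0.3 points of power. Being a subgroup factor suggests possible effect modification, which is not evidence that insulin use predicts HbA1c once baseline HbA1c is known. All of this stands, and it limits the point to an efficiency.

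A reader might infer more, but the SAP does not support it:
- **That the trial lacks precision.** The 380 is a minimum with recruitment continuing, a correlation above 0.3 would raise power, and 12.6 describes the single-timepoint calculation as conservative for the repeated-measures model.
- **That insulin use goes unused.** It is summarised at baseline, is a subgroup interaction in the refitted primary model, and is a descriptive secondary outcome.
- **That omission biases the primary estimate.** Under randomisation it does not, and chance imbalance is already within the confidence interval.
- **That randomisation leaves insulin use unbalanced by design.** Section 10 is an extract from the protocol, and its silence on stratification settles nothing.

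There is also a fair objection on timing. Version 1 was signed in September 2024. Section 10 says the statisticians are not blind and would be kept from unblinded primary outcome data only until that sign-off. An unconditional change of primary model could look data-driven.

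**Conclusion.** The point holds as a low-cost improvement. The primary and imputation models omit two collected baseline variables that may be prognostic. The stated 88% power is correct and unaffected. For insulin use the gain at 380 randomised is about 0.3 to 3.5 points of power, equivalent to roughly 3 to 48 more participants. This assumes 20-40% users, a residual gap of 3-10 mmol/mol, and the plan's own SD, correlation, ICC and attrition. Nothing in the SAP shows where in that range the trial lies. No figure can be put on diabetes duration, so insulin use carries the case. Apart from power, prespecifying the covariate settles in advance how an imbalance in insulin use is handled.

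**What to change.** - **12.6:** add baseline insulin use (yes/no) as a fixed effect and, optionally, years since diabetes diagnosis. Define insulin use once, since 7.2 records self-reported use and 12.8 labels it as prescribed.
- **Missing covariate values:** state a simple rule, such as mean imputation or a missing category, which is acceptable for baseline covariates under randomisation. The SAP does not say how many values will be missing.
- **12.7.2:** add the same variables to the imputation model.
- **Section 13:** make the change as a dated log entry confirming that primary outcome data by arm had not been seen. Keep the current 12.6 model as a sensitivity row in Table 7.
- **If those data have been seen:** leave 12.6 as primary and report the covariate-adjusted model as a labelled sensitivity row.

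The cost is SAP wording, one or two further fixed-effect parameters, one row in Table 7 and the log entry. No new data are needed.

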12.9 Analysis of secondary outcomes

BMI, smoked at any point in the last 7 days (yes or no), BPRS scores, PHQ-9 scores and PAID-5 scale scores will be analysed using mixed effects regression analysis for continuous outcomes, and logistic mixed models for binary outcomes. Baseline scores, randomised treatment group, time and a treatment group-by-time interaction, sex and age will be included as fixed effects and participant and DIAMONDS coach as random effects (to reflect the primary analysis model). Models will include assessments at all available time-points and will provide an overall treatment effect over 12 months, as well as estimates at individual time-points (6 and 12 months), reported as estimates and 95% confidence intervals. Different covariance patterns for the repeated measurements will be explored, and the most appropriate pattern will be used for the final model.

Other secondary outcomes (total cholesterol, HDL cholesterol, triglycerides, LDL cholesterol, haemoglobin, systolic BP, diastolic BP, waist circumference, urinary albumin: creatinine ratio, insulin use, diabetes complications, EQ5D-5L scores, IPAQ levels and SDSCA category scores) will be presented descriptively by treatment arm.

Accelerometer data will be collected at baseline and 6-months post-randomisation. Data will be analysed using the R-package GGIR, which performs signal processing of the raw data, including auto-calibration, detection of abnormal values, detection of non-wear, and calculation of the average magnitude of dynamic acceleration (Euclidean norm minus one g [ENMO]). Files will then be exported to Stata or similar statistical software for further analysis. Descriptive statistics will be reported by treatment group at each time point (baseline and 6 months) and differences between treatment groups will be reported, adjusted for baseline.

Based in findings from the feasibility study, analysis will be restricted to participants who had at least 4 valid days of accelerometer monitoring (out of a planned 7 days). The following summaries will be presented by treatment arm for all days and split by weekdays and weekend days:

- Number of valid days the participants wore the accelerometer (n (%), mean (SD);
- Valid wear time in hours (mean and SD);
- Number and percentage of participants with the required number of valid days;
- Time spent engaging in light activity (minutes per day) (mean and SD);

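### The primary model gives baseline HbA1c a single slope for both visits; if the 6- and 12-month slopes differ, the 12-month contrast loses some precision and can be biased when baseline-related dropout also differs by arm

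*SAP*

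**What the plan says.** Section 12.6 specifies a partially nested mixed model "with HbA1c scores at 6- and 12-months follow-up as the dependent variable, adjusting for baseline HbA1c scores and outcome source". For the remaining fixed effects, "randomised treatment group, time and a treatment group-by-time interaction will be included as fixed effects". The treatment effect may therefore differ by visit, but no term lets the baseline effect do so. The target is the later visit alone: "The estimated treatment group difference at 12 months will be reported as the primary endpoint".

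One feature is left to the data: "Different covariance patterns for the repeated measurements will be explored and the most appropriate pattern will be used for the final model". That choice concerns the covariance only. The listed model checks (residual normality, homoskedasticity, variance inflation factors) do not compare baseline slopes, and the central-laboratory sensitivity analysis in 12.7.1 refits the same model.

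The revised calculation in section 9 makes an "adjustment for the correlation between baseline and 12-month HbA1c (0.3) to reflect the repeated measures analysis model planned for the primary analysis". Section 12.6 notes that this calculation compares the arms at 12 months only, and concludes: "This is a more conservative approach so we should still have adequate power for the primary analysis".

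The section 12.9 models have the same structure: "Baseline scores, randomised treatment group, time and a treatment group-by-time interaction, sex and age will be included as fixed effects".

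**The concern.** Correlation between repeated measurements usually weakens as the interval grows, so baseline HbA1c may well predict the 6-month value more strongly than the 12-month value. A single coefficient must then compromise between two different slopes. Under an unstructured covariance the compromise leans towards the 6-month slope, because the 6-month values have the smaller residual variance. The 12-month contrast is then over-adjusted for baseline.

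Two things are at stake. First, some variance that a 12-month-specific slope would remove stays in the primary contrast. Second, section 12.6 relies on outcomes being missing at random. Dropout that depends on observed baseline HbA1c, and does so differently in the two arms, meets that assumption, so the primary model ought to handle it. With the wrong slope it does not fully do so, because the completers' baselines differ between arms and the difference is over-corrected.

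**Working it through.** **Inputs from the SAP.** Difference 5.5 mmol/mol; SD 15.3; intraclass correlation 0.02 with 10 to 12 participants per coach, intervention arm only; 20% attrition; 1:1 allocation; two-sided 5%; baseline-to-12-month correlation 0.3; N = 380; stated power 88%.

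**Assumed, because the SAP does not give them.** Baseline-to-6-month correlation r6 from 0.3 to 0.7; 6-to-12-month correlation r612 from 0.5 to 0.7; equal SDs at all visits; the dropout patterns in step 3.

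**Step 1: the SAP's power.** With 11 participants per coach the design effect is 1 + 10 × 0.02 = 1.20, and there are 190 × 0.8 = 152 analysed per arm.

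- Variance of the difference = 15.3² × (1 − 0.3²) × (1 + 1.20) / 152 = 234.09 × 0.91 × 2.20 / 152 = 3.083, so SE = 1.756.
- Power = Φ(5.5/1.756 − 1.96) = Φ(1.172) = 87.95%.
- With 10 and 12 per coach it is 88.2% and 87.7%. The stated 88% is reproduced.

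**Step 2: precision under one common slope.** In SD units let v6 = 1 − r6², v12 = 0.91 and c = r612 − 0.3 × r6. The large-sample weight on the 6-month slope is w = (v12 − c)/(v6 + v12 − 2c) under an unstructured covariance, and 1/2 under compound symmetry. The common slope is b = w × r6 + (1 − w) × 0.3. The 12-month variance is multiplied by 1 + (b − 0.3)²/0.91, and power is Φ(5.5/(1.756 × √multiplier) − 1.96).

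Example, r6 = 0.6, r612 = 0.7, unstructured: v6 = 0.64; c = 0.70 − 0.18 = 0.52; w = 0.39/0.51 = 0.765; b = 0.529; multiplier = 1 + 0.229²/0.91 = 1.058; SE = 1.806; power = Φ(1.085) = 86.1%.

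Ranges cover both covariance patterns and r612 of 0.5 to 0.7:

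| r6 (assumed) | Common slope b (12-month slope is 0.30) | Extra 12-month variance | Power at N = 380 |
|---|---|---|---|
| 0.3 | 0.30 | 0% | 88.0% |
| 0.4 | 0.35–0.36 | 0.3% | about 87.8% |
| 0.5 | 0.40–0.43 | 1.1–1.8% | 87.6–87.4% |
| 0.6 | 0.45–0.53 | 2.5–5.8% | 87.2–86.1% |
| 0.7 | 0.50–0.68 | 4.4–16% | 86.6–82.8% |

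Geometric decay to 0.3 over two equal steps gives r6 = r612 = √0.3 = 0.55. Then, unstructured, v6 = 0.70, c = 0.55 − 0.3 × 0.55 = 0.38, w = 0.62, b = 0.455, extra variance 0.155²/0.91 = 2.6%, and power about 87.1%.

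**Step 3: bias.** Illustration: about 20% missing at 12 months, with dropout rising by 1 log-odds per SD of baseline in the intervention arm and unrelated to baseline in the control arm. Intervention completers then have a mean baseline about 2.65 mmol/mol lower than control completers. Under the unstructured model,

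bias ≈ 2.65 × [(b − 0.3) + (c/v6) × (r6 − b)].

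The second part arises because the 6-month residuals, which help to recover missing 12-month values, carry the slope error too. With r612 = 0.6:

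- r6 = 0.4: 2.65 × [0.054 + 0.571 × 0.046] = 0.21
- r6 = 0.5: 2.65 × [0.121 + 0.600 × 0.079] = 0.45
- r6 = 0.6: 2.65 × [0.207 + 0.656 × 0.093] = 0.71
- r6 = 0.7: 2.65 × [0.325 + 0.765 × 0.075] = 1.01

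Simulations (N = 380, 1,500 replicates per scenario, coach effect omitted, Monte Carlo error about 0.04) agree: 0.25 at r6 = 0.4, 0.40 to 0.41 at 0.5, 0.64 to 0.79 at 0.6, and 0.88 to 1.03 at 0.7. At 0.5 to 0.7, coverage of the 95% interval was 92% to 94%. In a harsher case, with dropout related to baseline in opposite directions in the two arms, bias was 0.8 at r6 = 0.5 and 1.8 at 0.7, where coverage fell to 81%.

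Bias stayed within Monte Carlo error (at most 0.04) with complete data, with completely random dropout, with dropout related to baseline identically in both arms, and whenever r6 = 0.3. With baseline-by-time in the model it was within about 0.05 in every scenario.

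**Step 4: the conservatism sentence.** With 20% random loss at 12 months and an unstructured covariance, simulated SEs for simple 12-month ANCOVA and for the common-slope model were 1.70 and 1.64 (r6 = 0.4), 1.65 and 1.62 (0.5), 1.70 and 1.68 (0.6), and 1.68 and 1.73 (0.7). Under compound symmetry at 0.7 they were 1.65 and 1.66. The Monte Carlo error of one such SE is about 1.67/√(2 × 1,500) = 0.03. A separate run gave 1.63 and 1.64 at 0.6, and 1.63 and 1.68 at 0.7.

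**The case against.** The strongest reply is that unequal slopes are an assumption. The SAP gives one correlation and no 6-month or 6-to-12-month value, and it does not announce a common slope; it simply lists no interaction. This stands, and the point is conditional for that reason.

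The larger figures also need somewhat strained inputs. When r6 × r612 exceeds 0.3 (for example 0.6 × 0.6 = 0.36), a higher baseline would predict a lower 12-month HbA1c at a given 6-month value. Ordinary decay points to about 0.55, where the cost is under one power point. Compound symmetry lowers it further, and 380 is a minimum that the sponsor intends to exceed.

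A reader might infer that baseline-related dropout in itself biases the primary estimate. It does not: bias needs unequal slopes and dropout whose relation to baseline differs by arm. The SAP gives no dropout pattern, so the 1 log-odds scenario is illustrative. At correlations of 0.4 to 0.5 the bias is under a third of one standard error.

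A reader might also infer that the conservatism sentence is false. The simulations do not support that: up to 0.6 the two SEs differ by little more than Monte Carlo error or favour the planned model, and a reversal is clear only near 0.7 with an unstructured covariance.

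Finally, 12.7.2 plans multiple imputation that retains imputed 12-month values, which would largely expose such a bias. It is conditional on being judged appropriate, and as a sensitivity analysis it leaves the primary model unchanged.

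**Conclusion.** The point holds as a conditional weakness of modest size. The primary model as written imposes one baseline slope on two visits, and nothing else in the plan frees it. The cost is zero if the slopes are equal, about 0 to 2 power points for a 6-month correlation up to 0.6, and about 1 to 5 points at 0.7. Bias of roughly 0.2 to 0.8 mmol/mol (4% to 15% of the 5.5 target), or about 1 at 0.7, arises only when the slopes differ and baseline-related dropout also differs by arm.

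The documents do not show that the primary estimate is biased or that the 88% is wrong. The conservatism statement holds over most of the range examined, but is not guaranteed near 0.7. These results rest on assumed 6-month and 6-to-12-month correlations, equal SDs and, for the slope and bias calculations, no coach effect. No calculation was made for the 12.9 outcomes.

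**What to change.** In 12.6, add a baseline HbA1c-by-time interaction as a fixed effect, so that baseline has its own coefficient at 6 and at 12 months. This costs one degree of freedom and needs no new data. It removes the equal-slopes assumption from the primary contrast and puts the power sentence on firmer ground. For consistency, add baseline score-by-time to the 12.9 models. Record the change in the SAP amendment log before the outcome data are analysed by arm.
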